#### **4.3. Enrollment Target and Study Duration**

- Approximately 32 subjects will be enrolled in the study with 24 targeted to complete the cohort. An attempt will be made to recruit subjects that have -1.00D to -1.50D of refractive cylinder in at least one eye and no greater than -1.50D in either eye.
- The study will take place at one site and have one study visit per subject. Each ECP will fit a maximum of 4 subjects.

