## SYNOPSIS

Protocol Title	Evaluation of the JJVC Investigational Toric Multifocal Contact Lens Fitting Guide Phase II
Sponsor	JJVC, [name]
Clinical Phase	Phase 2
Trial Registration	This study will be registered on ClinicalTrials.gov by the Sponsor
Test Article(s)	Investigational Products: etafilcon A Toric Multifocal Contact Lens Marketed Products: 1-Day Acuvue® Moist Brand Multifocal Contact Lens
Wear and Replacement Schedules	Wear Schedule: Daily Wear Replacement Schedule: None- Non-dispensing study
Objectives	The primary objective of this study is an evaluation of the JJVC Investigational Toric Multifocal and 1-Day Acuvue® Moist Brand Multifocal Contact Lens fitting guides by Eye Care Providers (ECPs).

[REDACTED] (5)

Study Endpoints	
Primary endpoint: The maximum number of lens modifications for both eyes required by the ECP to optimize the lenses for vision.
 
Secondary endpoint:
 
 
1. Subjective feedback from the ECP on the fitting guide process (i.e. intuitive nature of the fitting steps, adequate amount of information provided by the fitting guide, strengths and weaknesses, etc.)
 
2. Subjective feedback from the ECP regarding the layout of the fitting guide.
 
3. Surveys of the subjects experience.
 

Study Design	
This study is a single arm, non-randomized, open label, non-dispensing clinical trial. The key assessments for this study will be the number of fitting modifications and ECP feedback throughout the fit process while using the Fit Guide. Each ECP will fit at least 3 subjects and no more than 4.
 
See the flow chart at the end of the synopsis table for the schematic of the study visits and procedures of main observations.

Sample Size	
A total of approximately 32 subjects will be enrolled into the study. Approximately 24 are targeted to complete.

Study Duration	
The study duration is anticipated to be approximately 1 week.

Anticipated Study Population	
Healthy male and female volunteers with presbyopia will be screened as per criteria outlined below.

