## **1. INTRODUCTION AND BACKGROUND**

Johnson & Johnson Vision Care (JJVC) has recently launched a multifocal contact lens, 1-Day ACUVUE Moist Multifocal. The lens is indicated to correct  $\leq -0.75$  D of refractive cylinder. A significant number of presbyopic eyes have greater than -0.75 D of cylinder. With this in mind, JJVC has a toric multifocal lens development program to attempt to fill this need.

Historically ECPs have viewed multifocal lens fitting in general, and toric multifocal lens fitting in particular, as being difficult in terms of the excess time often required to ensure an acceptable level of vision. In addition to the extra time required to fit lenses there is often a low level of overall success. A key aspect of the fitting process is the fitting guide. The ideal fitting guide would be intuitive to the ECP, and by following the recommendations result in a high level of success, with a limited number of lens changes to reduce the time required with each patient. This study aims to evaluate the ECPs impression of the fitting guide for a novel multifocal toric lens and also their success in fitting the lenses.

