### **1.2. Intended Use of Investigational Products**

The toric lens product is indicated to correct presbyopic eyes that have between -1.00 and -1.50D of refractive cylinder. The Control lens is a marketed product and is indicated to be fit on presbyopic eyes that have -0.75D of cylinder or less.

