## **2. STUDY OBJECTIVES, ENDPOINTS AND HYPOTHESES**

### **2.1. Objectives**

#### **Primary Objective(s)**

The primary objective of this study is an evaluation of the JJVC Investigational Toric Multifocal and 1-Day Acuvue® Moist Brand Multifocal Contact Lens fitting guides by Eye Care Providers (ECPs).

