#### **3.2. Inclusion Criteria**

Potential subjects must satisfy all of the following criteria to be enrolled in the study:

1. The subject must read, understand, and sign the STATEMENT OF INFORMED CONSENT and receive a fully executed copy of the form
2. The subject must appear able and willing to adhere to the instructions set forth in this clinical protocol.
3. Healthy adult males or females that are at least 40 years of age and no more than 70 years of age.
4. The subject must either be wearing a presbyopic contact lens correction (e.g., reading spectacles over contact lenses, multifocal or monovision contact lenses, etc.) or if not respond positively to at least one symptom on the “Presbyopic Symptoms Questionnaire”.
5. The subject is a current soft spherical or toric contact lens wearer (defined as a minimum of 6 hours of wear per day at least two days of the week for a minimum of 1 month prior to the study).
6. The subject’s distance spherical equivalent or spherical component (if the eye has -1.00 to -1.50 D of refractive cylinder) of their refraction must be in the range -1.25 D to -3.75 D or +1.25 D to +3.75 D in each eye.
7. The subject’s refractive cylinder cannot be greater than -1.50D in either eye.
8. The subject’s refractive cylinder axis must be  $90^\circ \pm 30^\circ$  or  $180^\circ \pm 30^\circ$  in each eye.
9. The subject’s ADD power must be in the range of +0.75 D to +2.50 D in each eye.
10. The subject must have best corrected visual acuity of 20/20^3 or better in each eye.
11. The subject must have a wearable pair of spectacles if required for their distance vision.

████████ (5)

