#### **4.2. Study Design Rationale**

The primary aim of the study is to obtain ECP feedback on the fitting process of the lenses. With this aim in mind, the study design attempts to create the typical multifocal contact lens fitting scenario encountered in routine clinical practice. The primary purpose of the study is to obtain feedback on the ease of fitting and fitting guide for the multifocal toric lenses and as such there is no need for a Control lens or masking of any of the study personnel.

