## 14. STATISTICAL METHODS

### 14.1. General Considerations

All data summaries and statistical analyses will be performed using the SAS software Version 9.4 (SAS Institute, Cary, NC). Throughout the analysis of data, the results for each subject/eye will be used when available for summarization and statistical analysis. Unscheduled visits will be summarized separately and will be excluded from the statistical analysis.

Summary tables (Descriptive statistics and/or frequency tables) will be provided for all baseline variables, efficacy variables and safety variables as appropriate. Continuous variables will be summarized with descriptive statistics (n, mean, standard deviation (SD), median, minimum and maximum). Frequency count and percentage of subjects or eyes within each category will be provided for categorical data.

Summaries will be presented by study lens type and will be performed separately by completion status. All analyses will be conducted on per-protocol population (see section 14.3).

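### A pass on the pooled 50% rule cannot show that the toric guide meets the threshold: no minimum number of toric subjects is set, and the primary test is not split by lens

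*Combined protocol and SAP*

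**What the plan says.** **Purpose.** Three places point to the toric lens alone. The title in the Synopsis is "Evaluation of the JJVC Investigational Toric Multifocal Contact Lens Fitting Guide Phase II". Section 1 says "This study aims to evaluate the ECPs impression of the fitting guide for a novel multifocal toric lens". Section 4.2 says "The primary purpose of the study is to obtain feedback on the ease of fitting and fitting guide for the multifocal toric lenses". The formal primary objective (Synopsis and Section 2.1) is wider: "an evaluation of the JJVC Investigational Toric Multifocal and 1-Day Acuvue® Moist Brand Multifocal Contact Lens fitting guides".

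**Who can enter.** On the amount of cylinder, inclusion criterion 7 in Section 3.2 gives only an upper limit: "refractive cylinder cannot be greater than -1.50D in either eye". No criterion requires an eye in the toric range. Section 4.3 adds an intention without a quota or minimum: "An attempt will be made to recruit subjects that have -1.00D to -1.50D of refractive cylinder in at least one eye". Under Section 1.2 the toric lens is for eyes with -1.00 to -1.50 D of cylinder. For the other lens it says "The Control lens is a marketed product and is indicated to be fit on presbyopic eyes that have -0.75D of cylinder or less". A subject at -0.75 D or less in both eyes is therefore eligible and falls under the marketed lens only.

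**The test.** The hypothesis in Section 2.3 concerns the percentage of all subjects who need no more than one modification. Section 14.5 concludes superiority when the 95% interval for that percentage lies wholly above 50%. The model there has age, gender and add power as fixed effects, with ECP and subject as random effects. It has no term for lens type or cylinder. Section 14.1 says "Summaries will be presented by study lens type", but these summaries are not part of the success rule.

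**The endpoint.** The Synopsis takes the maximum number of modifications over both eyes. Section 2.2 describes the endpoint as the number of lenses needed.

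**The concern.** If the study is meant to inform on the toric guide, the primary conclusion should come from subjects to whom a toric lens was fitted. As written, subjects without a toric eye enter the numerator and denominator on equal terms, and the plan does not control how many there will be. If the marketed multifocal is easier to fit, the pooled proportion can clear 50% when the proportion among toric subjects does not. A reader of the report, guided by the title and Section 4.2, would then take a pooled pass as evidence for the toric guide.

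The lens-type summaries in Section 14.1 do not close the gap. They are descriptive, and the primary outcome is one value per subject. A subject with a toric lens in one eye and the marketed lens in the other has no defined category.

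**Working it through.** **Inputs from the documents:** 24 completers (Sections 4.3 and 14.2); null value 50% (Section 2.3); success when the lower 95% limit exceeds 50% (Section 14.5).

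**Inputs assumed:** the number of toric subjects *m* and the success rates by lens, neither of which is given. Here a toric subject wears a toric lens in at least one eye. Toric subjects are set at the null 50%, and non-toric subjects at 70%, 80%, 90% and 95%. Subjects are treated as independent, ignoring clustering by ECP.

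**1. The plan's own figures.** The power table in Section 14.2 reproduces with an exact one-sided 5% binomial test against 50%:
- n = 56, at least 35 successes, true 70%: power 0.913
- n = 35, at least 23, true 75%: 0.924
- n = 23, at least 16, true 80%: 0.928

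All three match. Each row takes a single success rate for all subjects, so the table says nothing about a mixture of lenses.

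**2. Successes needed among 24.** With the exact interval, 17/24 has a lower limit of 0.489 and 18/24 has 0.533, so 18 are needed. With the Agresti-Coull interval, 16/24 gives 0.466 and 17/24 gives 0.506, so 17 are needed. Section 14.5 leaves the final interval method open, so both are shown.

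**3. Chance of a pooled pass.** Let X ~ Bin(m, 0.50) be the toric successes, Y ~ Bin(24 - m, p) the non-toric successes and c the number needed:

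P(pass) = Σₓ C(m, x) 0.5^m × P(Y ≥ c - x)

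Check at m = 24, c = 18: (134596 + 42504 + 10626 + 2024 + 276 + 24 + 1) / 2^24 = 190051 / 16777216 = 0.011.

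| Toric subjects of 24 | c = 18; p = 70 / 80 / 90 / 95% | c = 17; p = 70 / 80 / 90 / 95% |
|---|---|---|
| 24 | 1.1% | 3.2% |
| 20 | 2.4 / 3.3 / 4.4 / 5.1% | 6.1 / 8.1 / 10.4 / 11.7% |
| 18 | 3.4 / 5.4 / 8.2 / 9.9% | 8.3 / 12.3 / 17.5 / 20.6% |
| 12 | 9.1 / 19.7 / 37.0 / 48.4% | 18.6 / 34.8 / 56.6 / 68.7% |
| 8 | 16.0 / 38.1 / 69.5 / 84.9% | 29.2 / 56.6 / 84.9 / 94.6% |

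**4. One possible data set.** Six of 12 toric subjects succeed and 12 of 12 non-toric subjects succeed. Pooled, this is 18/24 with a lower limit of 0.533, so the rule is met. The toric group alone is at 50%, with an exact 95% interval of 21% to 79%.

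**5. Mixed subjects.** If the endpoint is the maximum over both eyes, as in the Synopsis, a toric eye that needs more than one modification makes the subject a failure whatever the other eye does. The dilution then comes mainly from subjects with no toric eye.

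**6. Precision of a toric-only estimate.** Exact two-sided 95% rule, true rate 80%:
- 24 toric completers: 18 needed, power 0.81
- 18 toric completers: 14 needed, power 0.72
- 12 toric completers: 10 needed, power 0.56

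**The case against.** The strongest reply is that the formal objective names both guides, the hypothesis speaks of subjects without restriction, and Section 14.5 tests exactly that. On this reading pooling is the planned analysis and not a mistake. That stands, and it is why the pooled proportion should be kept. It does not make one combined proportion informative about either guide separately.

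Second, Section 4.2 speaks of feedback, Section 14.2 says the sample size does not rest on a power analysis, and nowhere do the documents state that passing the test supports a toric-only claim. This is also true. A reader might infer such a claim from the title and Section 4.2; the plan should rule that inference out.

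Third, recruitment aims at subjects with a toric-range eye. If it largely succeeds the effect is small: with 20 of 24 toric it is 2-5% when 18 successes are needed and 6-12% when 17 are needed. Nothing in the plan secures that share, however.

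Fourth, the fitting guides in Appendices F and G are blacked out. If one guide covers both lenses, the pooled rate does describe that guide. The proportion in toric subjects would still be what answers the purpose in Section 4.2.

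Two stronger readings are tempting. One is that the marketed lens can mask failures in subjects wearing one lens of each kind; the both-eyes maximum in the Synopsis does not support that. The other is that the trial has a false-success risk of 37% or 70%. Those values require non-toric success of 90% against 50% in toric subjects, and 12 or 8 toric subjects out of 24. The documents support neither the contrast nor those shares.

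**Conclusion.** The concern holds in a limited form. The documents disagree on whether the study concerns the toric guide or both guides. They set no minimum number of toric subjects, and they base the only formal decision on a pooled proportion. A pooled pass therefore cannot show that the toric guide meets the 50% threshold.

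The size is conditional. With toric subjects at 50% and non-toric subjects at 70-95%, the chance of a pass when 18 successes are needed is 1% with 24 toric subjects, 2-5% with 20, 3-10% with 18, 9-48% with 12 and 16-85% with 8. When 17 are needed it is 3%, 6-12%, 8-21%, 19-69% and 29-95%. These figures rest on 24 independent completers and on assumed rates and shares. The statement about mixed subjects also requires the Synopsis definition of the endpoint. It does not follow that the pooled analysis is invalid for the objective in Section 2.1.

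**What to change.** 1. Reconcile the primary objective in the Synopsis and Section 2.1 with the title, Section 1 and Section 4.2, so that it is clear whether one guide or both are being evaluated.
2. In Section 14.5, keep the pooled proportion for the both-guides objective. Prespecify the success proportion, its 95% interval and the number of subjects separately for two groups: subjects fitted with a toric lens in at least one eye, and subjects with no toric lens. This also gives mixed subjects a defined category.
3. State in Section 14.5 that any conclusion about the toric guide rests on the any-toric group and not on the pooled result.

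Eligibility and conduct need not change. The cost is a few sentences and one extra table. The downside is a wider interval in the toric group if it has fewer than 24 completers, with the loss of power shown in step 6 of the working.

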### **5. TEST ARTICLE ALLOCATION AND MASKING**

#### **5.1. Test Article Allocation**

The study is a single-ARM trial.

#### **5.2. Masking**

The study is open label with no masking. Subjects will be aware of the identity of the investigational product. Investigators and clinical site personnel involved in the data collection will not be masked as to the identity of the investigational product.

#### **5.3. Procedures for Maintaining and Breaking Randomization Codes**

There is no masking or randomization for this study.

[REDACTED] (5)

## 6. STUDY INTERVENTION

### 6.1. Identity of Test Articles

[figure not shown]
[figure not shown]
[figure not shown]
The following contact lenses will be used in this study:

Table 1: Test Articles

Name	JJVC Investigational Toric Multifocal Contact Lens for Presbyopia	1-Day Acuvue® Moist Brand Multifocal Contact Lens
Manufacturer	Johnson & Johnson® Vision Care, Inc.	Johnson & Johnson® Vision Care, Inc.
Compass Protocol(s) and/or Lot Number or Other Identifier	
████████ Over labeling  ████████ (minus lenses, LOW, MID, HIGH)
 
████████ and Over Labeling  ████████ (plus lenses, LOW, MID, HIGH)
 
For the specific clinical build numbers see the tables listed below.
	
████████ Over labeling  ████████ (LOW, MID, HIGH)

Lens Material	etafilcon A	etafilcon A
Nominal Base Curve @ 22 °C	8.5	8.4
Nominal Diameter @ 22 °C	14.5	14.3
Nominal Distance Powers (D)	-1.00D to -4.00D and +1.00D to +4.00D in 0.25D steps	-1.00D to -4.00D and +1.00D to +4.00D in 0.25D steps
Nominal Cylinder Powers (D) and Axes	
-1.00D Cylinder Axes for myopic powers: 10°, 20°, 70°, 80°, 90°, 100°, 110°, 160°, 170°, 180°
 
Axes for hyperopic powers: 20°, 70°, 90°, 110°, 160°, 180°
	Not Applicable
Nominal ADD Powers (D)	LOW, MID, HIGH	LOW, MID, HIGH

████████ (5)

Nominal Water Content	58%	58%
Oxygen Permeability (Dk) (boundry corrected, non-edge corrected)	28.0	28.0
Modality in Current Study	Daily Wear	Daily Wear
Replacement Frequency	Daily Disposable	Daily Disposable
Packaging Form (vial, blister, etc.)	Blister	Blister

████████ (5)

Approximately 96 lenses will be used assuming an average of 2 pairs of lenses for each of the 24 subjects. The variation in lens usage will be due to determination whether or not optimization is required.

#### **6.2. Ancillary Supplies/Products**

The following solutions will be used in this study:

Table 2: Ancillary Supplies

[figure not shown]
Solution	
Solution Name/Description	Eye-Cept® Rewetting Drops
Manufacturer	Non-preserved
Preservative	Optics Laboratory

#### **6.3. Administration of Test Articles**

Test articles will be dispensed to subject meeting all eligibility requirements, including any dispensing requirements set forth in this clinical protocol. Subjects will be dispensed an adequate supply of Test articles to complete the study. Lost or damaged Test articles may be replaced at the discretion of the Investigator and/or the Sponsor.

#### **6.4. Packaging and Labeling**

The Test articles will be packaged in blisters as the primary packaging. The sample study label is shown below:

[REDACTED] (5)

## **6.5. Storage Conditions**

Test articles will be maintained at ambient temperatures at the clinical site. Test articles must be kept under secure conditions.

## **6.6. Collection and Storage of Samples**

Test articles will be disposed of after use and not collected unless associated with an Adverse Event. When possible, any lens or Test article associated with an Adverse Events and/or a Product Quality Complaint must be retained and stored in a glass vial with moderate solution pending directions from the sponsor for potential return back to JJVC.

## **6.7. Accountability of Test Articles**

JJVC will provide the Investigator with sufficient quantities of study articles and supplies to complete the investigation. The Investigator is asked to retain all lens shipment documentation for the Test article accountability records.

Test article must be kept in a locked storage cabinet, accessible only to those assigned by the Investigator for dispensing. The Investigator may delegate this activity to authorized study site personnel listed on the Site Delegation Log. All Test articles must be accounted. This includes:

1. What was dispensed for the subject for trial fitting, to wear out of the office, or issued for the subject to replace appropriately between visits
2. What was returned to the Investigator unused
3. The number and reason for unplanned replacements.

The Investigator will collect all unused Test articles from the subjects at the end of the subject's participation. Subject returned unused Test articles must be separated from the clinical study inventory of un-dispensed Test articles, and must be labeled with the subject number and date of return. Following final reconciliation of Test articles by the monitor, the Investigator or monitor will package and return all unused Test articles to JJVC.

If there is a discrepancy between the shipment documents and the contents, contact the study monitor immediately.

Reference [REDACTED]: Site Instructions for Test Article Receipt and Test Article Accountability for additional information.

[REDACTED] (5)

## 7. STUDY EVALUATIONS

### 7.1. Time and Event Schedule

Table 3: Time and Events

Visit Information	Visit 1 Screening, Baseline, Treatment 1
Time Point	Day 1
Estimated Visit Duration	5 hours
Statement of Informed Consent	X
Demographics	X
Medical History/Concomitant Medications	X
Habitual Contact Lens Information	X
Contact Lens History	X
Screening Inclusion/Exclusion Criteria	X
Subject Reported Ocular Symptoms	X
Entrance Snellen Distance Visual Acuity	X
Lens Removal	X
Subjective Sphero-Cylindrical Refraction	X
Near Add Determination	X
Ocular Dominance	X
Add Refinement	X
Near Visual Acuity	X

████████ (5)

Visit Information	Visit 1 Screening, Baseline, Treatment 1
Time Point	Day 1
Estimated Visit Duration	5 hours
Biomicroscopy	X
Baseline	X
Inclusion/Exclusion	
Lens Selection	X
ECP Global ID	X
Lens Insertion	X
Toric Fit (if Applicable)	X
Lens Fit Assessment	X
15 Minute Settling	X
ECP Fitting with Fit Guide	X
Modifications (if necessary)	X
Post-Fit Questionnaire	X
Exit Biomicroscopy	X
Final Evaluation	X
ECP Interview	X

## 7.2. Detailed Study Procedures

### VISIT 1

Visit 1: Screening			
Step	Procedure	Details	
1.1	Statement of Informed Consent	Each subject must read, understand, and sign the Statement of Informed Consent before being enrolled into the study. The Principal Investigator or his/her designee conducting the informed consent discussion must also sign the consent form. Note: The subject must be provided a signed copy of this document.	
1.2	Demographics	Record the subject's date of birth, gender, race	

(5)

		and ethnicity.	
1.3	Medical History and Concomitant Medications	Questions regarding the subjects' medical history and concomitant medications.	
1.4	Habitual Lenses	Questions regarding the subject's habitual lens type and parameters.	
1.5	Contact Lens History	Record the subject's correction type (i.e. monovision, multifocal, sphere with readers, etc.).	
1.6	Eligibility after Screening	All responses to Screening Inclusion Criteria questions must be answered "yes" and all responses to Exclusion Criteria must be answered "no" for the subject to be considered eligible.	

Visit 1: Baseline		
Step	Procedure	Details
1.7	Ocular Symptoms	If the subject reports ocular symptoms with their lenses they will be recorded in the Subject Reported Ocular Symptom Questionnaire
1.8	Entrance Visual Acuity	Distance and near Snellen visual acuity will be measured for each eye with the subject's correction in place. For near measures use the ETDRS 2000 Series Chart 1 or 2. The acuity will be recorded to the nearest letter OD, OS and OU.
1.9	Lens Removal (if applicable)	Have the subject remove their habitual lenses and store in an approved storage solution
1.10	Subjective Sphero-cylindrical Refraction	Complete optimal binocular balanced sphero-cylindrical refraction and record the resultant distance visual acuity (OD, OS and OU) to the nearest letter.  Note: Best distance visual acuity with sphero-cylindrical refraction must be at least 20/20^3 in each eye for the subject to enroll in the study.
1.11	Near Add Determination	The near reading addition will be determined using the binocular crossed cylinder technique at 40 cm followed by optimization in a trial

		frame in step 1.13 below.	
1.12	Ocular Dominance	Determine the distance ocular dominance with the best distance correction in place using a +1.00 blur test. If the results are equivocal use the sighting dominance test to determine the dominant eye used for the study.	Appendix E
1.13	Add Refinement	Place the BCC result in the trial frame and refine the near prescription with trial lenses (or flippers) under binocular conditions.	
1.14	Near Visual Acuity	Using the ETDRS 2000 Series Chart 1 or 2 near card placed at 40 cm. Record the near visual acuity OD, OS and OU at 40 cm.	
1.15	Biomicroscopy	
FDA Slit Lamp Classification Scale will be used to grade the findings and determine eligibility.
 
For the conjunctival redness [REDACTED] 0.5 unit increments will be used in the grading. Corneal Staining Assessment [REDACTED] will be graded in 1.0 increments.
 
If any of these slit lamp findings are Grade 3 or higher, the subject will be discontinued. If discontinued a final examination must be completed.
 
If the clearance of the fluorescein needs to be expedited, preservative-free rewetting drops or saline may be instilled.
	
1.16	Eligibility after Baseline	All responses to Inclusion Criteria questions must be answered "yes" and all responses to Exclusion Criteria questions must be answered "no" for the subject to be considered eligible.	

Visit 1: Treatment 1 Lens Fitting			
Step	Procedure	Details	
1.17	ECP Global ID	ADD the ECP's global ID.	
1.18	ECP Lens Selection	The ECP will be provided with the fitting guide and determine the initial study lens selection. The study staff will select the lens pair and power for each eye. Record the test	Appendix F/G Fitting Guides

		lens parameters (power and lot number).	
1.19	Lens insertion	
Subjects will insert the lenses themselves. If the lens is uncomfortable, inspect for damage and remove, reinsert or replace as necessary. Damaged lenses will be stored in labeled vial with sterile saline, and clearly differentiated from the other worn lenses that will be shipped back to the Sponsor. Complete the Quality Product Complaint form.
	
1.20	Toric Fit Evaluation (if applicable)	
The principal or Co-Investigator will evaluate the toric fit and record:
 
 
• The rotational position to the nearest degree
 
• Lens stability with blink
 
• Lens stability with eye versions
 
• Toric fit acceptable or unacceptable
 
 
Toric lens fit will be unacceptable if lenses rotated more than 40 degrees, or lens stability is worse than 5 degrees movement with blink. If toric fit is unacceptable, remove the lenses, perform biomicroscopy and proceed to final evaluation.
	
1.21	Lens Fit Assessment	
The principal or Co-Investigator will evaluate the general lens fit. Lens fit will be assessed in primary gaze, upgaze & Josephson push up test.
 
An unacceptable lens fit will be any one or more of the following:
 
 
• presence of limbal exposure (appearance of clear cornea) in any gaze
 
• presence of edge lift
 
• Presence of unacceptable movement (excessive or insufficient) in all three movement categories (primary gaze, upgaze, and push-up).
 
 
If either lens is deemed unacceptable, the subject will be discontinued from the study. Perform a slit-lamp evaluation and complete the Final Evaluation
	

████████ (5)

1.22	Lens Settling	Allow the study lenses to continue to settle for a minimum of 15 minutes from the time of lens insertion	
1.23	ECP Fitting with Fit Guide	The ECP will be provided the fitting guides and assess the vision provided by the lenses and will determine if a lens change is needed. The fitting activities of the ECP will be videotaped. During the fitting of the lenses the ECP may use the slit lamp to evaluate the fit of the lens. .	Appendix F/G Fitting Guides
1.24	Modifications (if necessary)	If the ECP determines a change in lenses is required they will be allowed two Modifications. If modification is needed complete steps 1.18 to 1.19 for each lens change.	Appendix F/G Fitting Guides
1.25	Post-Fit Questionnaire	The subject will evaluate the vision characteristics, comfort characteristics, handling characteristics, and visual symptoms of the study lenses using the PRO questionnaire. Subjects will also be shown a product concept of the lens they have just worn and their feedback regarding the concept will be collected.	Appendix A and H
1.26	Exit Biomicroscopy	The Principal Investigator or Co-Investigator will perform biomicroscopy OD and OS. Slit Lamp Classification Scales will be used to grade the findings. For the conjunctival redness [REDACTED] 0.5 unit increments will be used in the grading. Corneal Staining Assessment [REDACTED] will be graded in 1.0 increments.	[REDACTED]
1.27	ECP Interview	The ECP will be interviewed regarding their experience fitting the subject using the Fit Guide.	Appendix I

